There are minimal risks to participants in this study. BSS has been marketed in the United States for over 100 years, and is widely available without a prescription. It has a good safety profile at the recommended dose and duration of use. We will not exceed these safe dosing ranges in this study. The maximum daily dose (4.2g per day) of BSS results in peak serum concentrations of salicylate considerably below toxicity levels. This dose has been documented to be safely used for up to 3–4 weeks (26). We will include only adult participants and exclude children <18 years of age or elderly adults 70 years of age or older, pregnant or breastfeeding women, participants with a known contraindication to BSS use, or anyone taking medications known to interact with BSS, including other salicylate-containing compounds. Participants will be asked to refrain from taking aspirin or aspirin-containing compounds. The duration of BSS administration in this study will be limited to a maximum of 21 days.

BSS lists possible side effects on its packaging (including, but not limited to, constipation and tinnitus) that will all be discussed with the participant before informed consent and enrollment.

Participants will be provided contact information for study personnel at The New York Center for Travel and Tropical Medicine in the event that they have questions regarding the study or the medications before, during, or after travel. They will be notified to contact study personnel at The New York Center for Travel and Tropical Medicine in the event that they experience any adverse events of BSS or symptoms of TD.

In addition to the study preparations (BSS or placebo tablets), participants may also be provided with an appropriate medication for TD self-treatment (at the discretion of the healthcare provider) to carry with them in the event they develop TD while abroad. If they experience an episode of TD, they will be instructed to continue their study medication. Participants will also be counseled on hydration, the indications for antibiotic use (*i.e.*, in the event of severe diarrhea, but not mild or moderate diarrhea), and when to seek healthcare.

Each participant's confidentiality will be rigorously maintained (see Procedures for Implementing and Documenting Informed Consent). If a breech occurs, the IRB will be notified immediately and standard procedures will be followed.

Description of Anticipated Benefits to the Participant

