Includes the 7 days prior to departure in which the pre-travel questionnaire and a biologic (stool) specimen is collected, the full duration of travel, and through 10 days maximum post-return from travel, or until both the post-travel questionnaire and submission of the post-travel biologic (stool) specimen is complete (a maximum of 17 days post-travel)

Travel companion (group):

Two or more study participants with a common relation (friends, colleagues, or relatives) with the same itinerary, who anticipate performing the same activities during travel

Trip duration:

The number of days spent in country; excludes air travel time

Severe TD:

Hospitalization to an inpatient ward either during travel or after travel with a diagnosis of diarrhea

Acquisition of AMR gene(s):

The presence in a post-travel biologic (stool) specimen of one or more antimicrobial resistance gene(s) that were not present in a pre-travel biologic (stool) specimen from the same person, and which is known to confer antimicrobial resistance to one or more antimicrobial agents ("resistome")

Medication compliance:

Full = participant takes all scheduled doses according to directions

Good = If <15% of BSS or placebo doses were missed during travel

Fair = If 15–30% of BSS or placebo doses were missed during travel

Poor = If >30% of doses were missed during travel

Questionnaire compliance:

Full = participant completes all questionnaires

Good = participant completes >80% of all during travel questionnaires, AND
both the pre- and post-travel questionnaires

Fair = participant completes between 30–80% of all during travel
questionnaires, including AT LEAST the pre-travel questionnaire

Poor = participant completes <40% of all during travel questionnaires, and AT
LEAST the pre-travel questionnaire

Biologic (stool) specimen compliance:

Full = BOTH specimens collected and sent

Fair = ONLY one specimen collected and sent

Poor = No specimens collected and sent

Loss to follow-up:

Failure to complete the post-travel questionnaire after three attempts to contact the participant or if submission of the post-travel biologic specimen (stool) occurs more than 10 days after return from travel or is not submitted

Participant Inclusion Criteria

Willing participants must meet the inclusion criteria as outlined here:

1. Be ≥ 18 and <70 years of age at the time of enrollment

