2. Sign an informed consent (see Procedures for Implementing and Documenting Informed Consent) stating willingness to participate and comply with the study protocol
3. Plan on leaving for an international trip ≥ 7 days after their pre-travel consultation
4. Plan on traveling in country for ≥ 7 days but ≤ 21 days (21 day limit due to BSS duration recommendations and a lack of data on longer-term BSS use) (see Definitions)
5. Traveling to either South East Asia, South Central Asia, North Africa, or Sub-Saharan Africa for at least 7 days of their itinerary (see **APPENDIX B** for list of countries classified to each region)
6. Be willing to complete an initial eligibility screening (see Recruitment and Enrollment)
7. Be willing to complete questionnaires and provide biologic specimens (stool) within 7 days of departure and within 10 days after return
8. Be willing to refrain from taking any pre-biotics, probiotics, synbiotics and/or herbal supplements throughout their study period

Participant Exclusion Criteria

Willing participants must not meet any exclusion criteria as outlined here:

1. Are <18 years of age or >69 years of age
2. Are traveling in country for <7 or >21 days (see Definitions)
3. Have known or suspected contraindications to taking BSS (including, but not limited to, travelers with kidney disease, diabetes, gout, a clotting disorder, or an allergy to any component of BSS)

4. Are pregnant (via self-report), are planning to become pregnant, or may become pregnant during travel (not actively using contraception and are sexually active), or are breastfeeding
5. Routinely take a medication known to interact with BSS (including, but not limited to, insulin, methotrexate, valproic acid, ACE inhibitors, anticoagulants, or other salicylates) (see **APPENDIX A** for complete list)
6. Have taken an antibiotic in the 30 days before departure
7. Have taken any medications that may lower one's ability to fight infection (e.g., steroids, monoclonal antibodies, etc.)
8. Have previous diagnoses of immunocompromising conditions such as HIV/AIDS, complement deficiency, immunoglobulin deficiency, or undergoing active chemotherapy or participants with chronic gastrointestinal disorders, such as chronic diarrhea, irritable bowel syndrome (IBS), inflammatory bowel disease (i.e., Crohn's disease, ulcerative colitis), celiac disease, malabsorption syndromes, pancreatic insufficiency, gallbladder disease, or current gastrointestinal cancer

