Dosing will begin on the flight prior to arrival in the destination and will cease once they return home. The study medications must be taken twice daily (a morning and an evening dose); with time zone changes, the first dose should be taken to ensure that no longer than 12 hours passes before a subsequent dose.

Before departure, participants will be provided, free of charge, all needed study medication for the duration of their trip. Participants will be encouraged to take all doses of their medication and appropriately document on their daily during travel questionnaires if a dose was missed or taken off schedule.

Outcomes

The outcomes of this study will include:

	Favorable Outcome	Non-favorable Outcome
Hypothesis 1: Prevention of TD	Prevention of TD in the intervention group	TD in the intervention group at a rate similar to placebo; intervention drug side effects; adverse events

Hypothesis 2: Acquisition of AMR genes	Reduced or no presence of travel-associated gut AMR genes in the intervention group	No reduction in the presence of travel-associated gut AMR genes in the intervention group
---	---	---

The participant's study period will end in the following circumstances:

1. The traveler meets criteria for removal (see Criteria for Removal from the Study)
2. The participant voluntarily withdraws from the study (see Procedures for Implementing and Documenting Informed Consent)
3. The participant completes all study activities and submits all study questionnaires and biologic (stool) specimens
4. The participant is lost to follow-up

The participants will be instructed at enrollment to stop the study medication for any of the following reasons (although they will still be instructed to answer their questionnaires and submit biologic [stool] specimens as scheduled):

1. Antibiotics or BSS (either provided by the study personnel for TD treatment, or taken as an over-the-counter remedy) are taken for TD or for another medical condition
2. Any severe adverse events as described, such as signs and symptoms of salicylism or neurotoxicity, occur
3. Hospitalization for any reason

Barring the reasons listed above, the study medication should be taken throughout the trip duration, even if diarrhea occurs, if possible.

Criteria for Removal from the Study

Participants will be removed from the study when any of the following criteria apply:

1. Do not complete the pre-travel questionnaire (see Definitions for compliance)
2. Loss to follow-up (see Definitions)

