APPENDIX A: Screening Questionnaire

Screening Questionnaire

Script [read to all travelers]: Hello, my name is [name] and I am a [role in the clinic] at The New York Center for Travel and Tropical Medicine. We are conducting a study of international travelers to see if bismuth subsalicylate (or BSS) can help to prevent travelers' diarrhea. Participation in this questionnaire to see if you are eligible is voluntary, and it will only take a moment of your time. We will be collecting your email address, so in the event that you are eligible to participate, we can send you the study questionnaires and reminder emails; your email will only be used for study purposes. Are you interested in seeing if you are eligible to participate?

YES NO

[If "yes", please complete the following with the traveler]:

Participant's Initials		Date	
Age			

Participant Email (REQUIRED): _____
 Participant Phone #1 (OPTIONAL): _____ Participant Phone #2 (OPTIONAL): _____

1. Are you ≥ 18 years of age and <70 years of age?

Yes* No Don't know

2. Are you traveling to either South East Asia, South Central Asia, North Africa, or Sub-Saharan Africa?

Yes* No Don't know

3. Are you spending at least 7 days and no more than 21 days in these regions?

Yes* No Don't know

4. Are you leaving for your trip in at least 7 days?

Yes* No Don't know

5. Are you now pregnant or nursing or do you plan to get pregnant before the end of your trip?

Yes No* Don't know

6. Do you have known or suspected allergy to bismuth, salicylate, or aspirin?

Yes

No*

Don't know

7. Do you have known or suspected allergy to microcrystal cellulose, calcium carbonate, artificial coloring, magnesium, mannitol, povidone, saccharin, or talc?

Yes

No*

Don't know

8. Do you have kidney disease, diabetes, gout, or a clotting disorder?

Yes

No*

Don't know

9. Have you taken an antibiotic in the past 30 days? For example:

- Doxycycline or minocycline
- Flagyl, cotrimoxazole (e.g., Bactrim, Septra)
- Penicillins (e.g., amoxicillin, Augmentin)
- Cephalosporins (e.g., Keflex)
- Fluoroquinolones (e.g., ciprofloxacin)
- Macrolides (e.g., azithromycin [Zithromax], erythromycin)

Yes

No*

Don't know

10. Do you take any of the following medications or therapies?

- Chronic oral or intravenous IV steroids (e.g., hydrocortisone or prednisone); not inhaled steroids
- Alkylating agents (e.g., cyclophosphamide [Cytoxan])
- Antimetabolites (e.g., azathioprine [Imuran], 6-mercaptopurine [Purinethol])

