APPENDIX D: During-travel Questionnaire

During Travel Questionnaire

PARTICIPANT UNIQUE ID: _____

GROUP ID: _____

	Day 1	Day 2	Day 3	Day 4	Day 5
Please write the calendar date that corresponds to each day of your trip. Day 1 is your first day of arrival in the country.					
Number of tablets taken in the morning (maximum 4)					
Number of tablets taken in the afternoon/evening (maximum 4)					
Symptoms in the prior 24 hours (check off all that apply)	... 				
Fever					
Nausea					
Vomiting					
Loose stools (less than three in a 24 hour period)					
Diarrhea (three or more loose stools in 24 hours)					
Bloody diarrhea					
Constipation					
Dark or black stool					
Dark or black tongue					
Abdominal pain					
Abdominal cramps					
Urgency to relieve oneself (in reference to stool)					
Bloating					
Flatulence/gas					
Congestion/runny nose					
Sore throat					
Cough					
Rash					
Headache					
Dizziness					
Ringing in your ears					
Muscle pain/soreness					
Joint pain/swelling/redness					

Drowsiness (severe)					
Confusion					
Depression					
Other (list/describe):					
Medical care
Did you seek medical care for one or more of these symptoms? (Yes/No/Don't Know)	Y N D	Y N D	Y N D	Y N D	Y N D
→ If yes, where? (check the corresponding box(es))
A doctor's office					
Urgent care clinic (outpatient)					
Emergency room					
Hospital outpatient clinic setting					
Hospital inpatient ward – hospitalized					
Other (specify)					
→ Was your diagnosis travelers' diarrhea? (Yes/No/Don't Know)	Y N D	Y N D	Y N D	Y N D	Y N D
Have you started any medications in the past 24 hours? (Yes/No/Don't Know)	Y N D	Y N D	Y N D	Y N D	Y N D
→ If yes, what medication(s)?					
→ Please circle those that were provided for you at your pre-travel consultation with the study clinic.

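### The stated 21-day maximum for BSS is not guaranteed, because dosing, eligibility, the screener and the printed diary each count a different period

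*Combined protocol and SAP*

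**What the plan says.** Description of Risks to the Participant sets the limit: "The duration of BSS administration in this study will be limited to a maximum of 21 days". Inclusion criterion 4 ties the eligibility limit to the same reason: "Plan on traveling in country for ≥ 7 days but ≤ 21 days (21 day limit due to BSS duration recommendations". Exclusion criterion 2 mirrors it: "Are traveling in country for <7 or >21 days (see Definitions". The Definitions section says what trip duration counts: "The number of days spent in country; excludes air travel time".

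The Intervention section sets the dosing period: "Dosing will begin on the flight prior to arrival in the destination and will cease once they return home". Doses are twice daily, and the first is to be timed so that "no longer than 12 hours passes before a subsequent dose". The same section supplies enough tablets for the whole trip. Under Outcomes, participants are asked to keep taking the medication over the trip duration, which is the defined term that leaves flights out.

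Item 3 of the screener (Appendix A) asks: "Are you spending at least 7 days and no more than 21 days in these regions". Inclusion criterion 5 requires at least 7 days of the itinerary in those regions, so an itinerary may include other places. Item 9 of the pre-travel questionnaire (Appendix C) asks for total trip length, but no eligibility rule is attached to the answer.

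In the diary (Appendix D), "Day 1 is your first day of arrival in the country", and the last printed column is Day 21. The post-travel questionnaire (Appendix E) asks nothing about study tablets.

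**The concern.** The cap counts days on drug, the eligibility limit counts days in country, and the dosing instruction runs from flight to home. A participant at the eligibility limit who follows the dosing instruction can therefore pass a limit that the risk section presents as a safeguard. Nothing in the text available stops tablets at day 21.

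Two smaller matters follow. The screening form measures a different quantity from the criterion it applies. And the diary, which is the protocol's source for missed doses, lacks a place for some scheduled doses. That matters because Full compliance is defined as taking all scheduled doses, and the sample size is stated in terms of participants with full compliance.

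**Working it through.** **Inputs.** Cap 21 days (Description of Risks). Longest eligible stay 21 in-country days, flights not counted (criteria and Definitions). Dosing from outbound flight to home (Intervention). Four tablets twice daily (Intervention), 262 mg each (Cost Benefit). Printed diary of 5 + 5 + 5 + 5 + 1 = 21 columns, with a morning and an evening tablet count in each (Appendix D). Flight time is not in the documents; I assume 8 to 24 hours each way.

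**1. The plan's own figures.** 8 × 262 mg = 2,096 mg a day, which matches the stated 2.1 g. A 21-day cap is 21 × 2 = 42 doses, 42 × 4 = 168 tablets, or 168 × 0.262 = 44.0 g. The 21-day maximum is reproduced only if dosing is confined to in-country days, or if both the flight dose and the return home fall on dates already counted as Day 1 and Day 21.

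**2. Elapsed time at a 21-day stay.** Hours = 21 × 24 + time from first dose to landing + return flight. This treats the stay as 21 full 24-hour days.
- Low: first dose 1 hour before landing, 8-hour return. 504 + 1 + 8 = 513 h = 21.4 days.
- High: first dose at the start of a 24-hour outbound flight, 24-hour return. 504 + 24 + 24 = 552 h = 23.0 days.

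Doses, with the first at hour 0 and one every 12 hours, number hours ÷ 12 rounded up: 513/12 = 42.75, so 43; 552/12 = 46. The excess over 42 is 1 to 4 doses, or 4 to 16 tablets (1.0 to 4.2 g).

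**3. Calendar days at a 21-day stay.** Days = 21 + b + a, where b = 1 if the flight dose is dated before Day 1 and a = 1 if the return home is dated after Day 21 (at most one extra date at each end assumed). This gives 21, 22 or 23. At 23 days the maximum is 23 × 8 = 184 tablets (48.2 g).

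**4. Shorter stays.** With the longest assumed flights, 19 days give 19 × 24 + 48 = 504 h = 21.0 days, just at the cap; 20 days give 20 × 24 + 48 = 528 h = 22.0 days. The calendar count agrees: 19 + 2 = 21 and 20 + 2 = 22. Stays of 19 days or fewer remain within the cap.

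**5. Screener against criterion.** Exclusion 2 limits all in-country days to 21. Item 3 limits only days in the listed regions. A traveller with 21 listed-region days and further days elsewhere answers yes to item 3 although exclusion 2, on its natural reading, applies. The pre-departure call reviews the same screener answers.

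**6. Diary.** 21 columns × 2 = 42 dose slots. On the longest stay, 1 of 43 (2.3%) to 4 of 46 (8.7%) doses have no slot. On a 7-day stay, a first dose dated before arrival is 1 of 7 × 2 + 1 = 15 (6.7%). Each share is below the 15% boundary for Good compliance, so the gap mainly affects whether Full can be confirmed.

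**7. Sample size.** For 40% against 28%, two-sided 5% and 80% power, n = [1.960 × √(2 × 0.34 × 0.66) + 0.842 × √(0.40 × 0.60 + 0.28 × 0.72)]² / 0.12² = 243.4, so 244 per arm and 488 in all, as stated. Nothing here changes it.

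**The case against.** The strongest reply is that the cap survives on one available reading. The Outcomes section ties medication to trip duration, which by definition omits flights, and a 21-day stay can total 21 calendar days. Both statements are true. But that reading contradicts the flight-to-home rule in the Intervention section, so the plan disagrees with itself, and the cap then depends on which sentence a participant follows.

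A reader might infer from screener item 3 that someone with 21 days in a listed region and 7 elsewhere could be dosed for 28 days or more, at least 7 × 8 = 56 tablets over the cap. The documents do not support that as permitted conduct. Inclusion 4 and exclusion 2 limit in-country days separately from the regional requirement, Duration of Subject Involvement allows for 21 days of travel or less, and Appendix C collects days in every country and total trip length. What stands is that item 3 does not detect such a traveller and no stated rule acts on the total.

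A reader might also infer that flight doses are never recorded. That goes too far. A dose on the arrival date fits Day 1, spare columns on shorter trips can take return doses, and there is a Comments field. Daily data are collected mainly on the web, and the protocol says that the daily form captures date, time and number of tablets. The web form may differ from the printed layout, and the participant handout (Appendix K) and consent form (Appendix F) were not in the text available.

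**Conclusion.** The inconsistency is real and small. The plan states a 21-day maximum that its dosing period and eligibility count do not guarantee. The excess is 0 to 2 calendar days, or about 0.4 to 2.0 elapsed days (4 to 16 tablets), at a 21-day stay. It rests on the assumed 8 to 24 hours of flight each way. A 20-day stay can also pass the cap with long flights; shorter stays do not.

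Screener item 3 does not measure exclusion 2, and the printed diary cannot confirm Full compliance where a scheduled dose is dated before arrival or after Day 21.

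Two stronger conclusions should not be drawn. The cap is not bound to fail, since most eligible trip lengths stay within it. Nor is a hazard shown: the risk section itself reports documented safe use for 3 to 4 weeks at 4.2 g a day, twice the study dose. The conflict is with a stated limit.

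**What to change.** Reconcile Description of Risks, Definitions, inclusion 4, exclusion 2, Intervention and Outcomes so that the cap, the dosing start and stop, and the eligibility limit all use one clock. Which dosing period or limit applies is for the sponsor and investigators to decide.

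Reword screener item 3 to ask for the quantity in exclusion 2, and put the requirement of at least 7 days in the listed regions in a separate item. Add diary columns for outbound and return travel days, in the printed and web forms alike, so that every scheduled dose can be recorded.

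The cost is some wording, one changed and one added screener item, a few diary columns, and an IRB amendment, which the protocol already requires for changes to procedures or instruments. A few of the longest trips may change eligibility, depending on the clock chosen.
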